12. ETHICS AND REGULATORY REQUIREMENTS

This study is to be conducted in accordance with the specifications of this protocol and in accordance with principles consistent with Declaration of Helsinki, GCP, 21 CFR, ICH E6, HIPAA regulations in 45 CFR Part 164 (US only), and the Belmont Principles of respect for persons, beneficence, and justice. No protocol changes will be implemented without the prior review and approval of the IRB, except when the modification does not involve the subject's participation in the trial or where it may be necessary to eliminate an immediate hazard to a research subject. In the latter case, the change will be reported to the IRB as soon as possible, according to IRB regulations.

Additionally, the study product used in this study is manufactured, handled, and stored in accordance with applicable GMP. The study product provided for this study will be used only in accordance with this protocol.

12.1. INSTITUTIONAL REVIEW BOARD/INDEPENDENT ETHICS COMMITTEE (IRB/IEC)

The Principal Investigator (PI) at each site will provide the Institutional Review Board/Independent Ethics Committee (IRB/IEC) with all appropriate materials as required by their IRB/IEC, including but not limited to the clinical study protocol, informed consent form, and any advertising materials. The study will not be initiated until the IRB/IEC provides written approval of the aforementioned documents and until approval documents have been obtained by the Principal Investigator and Sponsor or Sponsor designee. The Investigator will not participate in the decision. If the Investigator is an IRB or IEC member, documentation must be provided indicating recusal from the approval process. Appropriate reports on the progress of this study by the Principal Investigator will be made to the IRB/IEC as required by local and applicable government regulations and in agreement with policy established by the Sponsor. The Investigator is required to maintain an accurate and complete record of all written correspondence to and received from the IRB/IEC and must agree to share all such documents and reports with the Sponsor.

No changes from the final approved protocol will be initiated without the IRB/IEC's prior written approval or favorable opinion of a written amendment, except when necessary to eliminate immediate hazards to the subjects or when the modification does not involve the subject's participation in the trial.

12.2. INVESTIGATOR'S RESPONSIBILITIES

The Investigators are responsible for performing the study in full accordance with the protocol and the current revision of the Declaration of Helsinki, the Good Clinical Practice: Consolidated Guideline, approved by the ICH, and any applicable national and local laws and regulations.

Information regarding to the study center participating in this study that cannot comply with these standards will be documented.

12.3. SUBJECT INFORMED CONSENT REQUIREMENTS

All subjects participating in this study will be given to by the Investigator and/or designee, written and oral information about the study in a language understandable by the subject. Written informed consent will be obtained from each subject prior to any procedures or assessments that would not otherwise be required for the care of the subject are done and after the aims, methods, anticipated benefits, potential hazards, and insurance arrangements in force are explained and the subject has been given sufficient time to ask questions and consider participation in the study. It will also be explained to the subjects that they are free to refuse entry into the study and free to withdraw from the study at any time without prejudice to future treatment. It is permissible for a third person (e.g., a family member) to be present during the explanation of the study.

The written Informed Consent Form (ICF) will be in compliance with CFR 21 Part 50.27 and GCP guidelines. The Sponsor and/or designated CRO will approve the ICF and all amendments to the ICF prior to submission to the IRB/IEC. A copy of the ICF to be used will be submitted by the Investigator to the IRB/IEC for review and approval prior to the start of the study. The study site must provide the Sponsor with an unsigned copy of IRB/IEC-approved ICF along with applicable documentation to support this approval. The original signed ICF is retained in the subject's study records, and a copy is provided to the subject. A second copy may be filed in the subject's medical record, if allowed by institutional policy.

13. DATA HANDLING AND RECORD KEEPING

13.1. Recording and Collection of Data

The primary source document for this study will be the subject's medical record. If separate research records are maintained by the Investigator(s), the medical record and the research records will be considered the source documents for the purposes of auditing the study.

Applicable source data will be manually transcribed to approve case report forms (CRF). The Investigator is ultimately responsible for the accuracy of the data transcribed on the forms. All source documents and CRFs will be completed as soon as possible after the subject's visit.

The Investigator will review the CRFs to indicate that, to his/her knowledge, they are complete and accurate. Designated source documents will be signed and dated by the appropriate study personnel. The Investigator must agree to complete and maintain source documents and CRFs for each subject participating in the study.

All research data will be entered, either electronically or manually, into a computerized database. The clinical database will be designed by the clinical data manager in accordance with 21 CFR Part 11 and based on protocol requirements defined by the Sponsor.

The Investigator will maintain a confidential list of study subjects that will include each subject's study number, name, date of birth, and unique hospital identification number if applicable. This list will be kept by the Investigator and will not be collected by the Sponsor. A notation will be made in the subject's case history/medical chart that he/she is participating in a clinical study and has provided a signed and dated ICF as well as a release for protected health information as required by local policies. The Investigator must also maintain a separate screening log of all the subjects screened for participation in the study; it should include gender, age, eligibility status, reason for ineligibility, if applicable; and study allocated subject number, if applicable.

13.2. CLINICAL DATA MANAGEMENT

The Sponsor and/or designated CRO will be responsible for the processing and quality control of the data. Data management will be carried out as described in the Sponsor's or CRO's standard operating procedures (SOPs) for clinical studies.

The handling of data, including data quality control, will comply with regulatory guidelines (e.g., ICH E6 GCP, and local regulations where applicable) and the Sponsor's or the CRO's SOPs as well as provisions of the study-specific Data Management Plan.

13.3. ARCHIVING

All study documentation at the Investigator site and Sponsor site will be archived in accordance with ICH GCP E6 and the Sponsor's quality standards and SOPs.

The Investigator will maintain all research records, reports, and case history reports for a period of two (2) years after regulatory approval of the investigational product. If no application is filed or if the application is not approved, records must be maintained for two (2) years after all investigations have been completed, terminated or discontinued and the FDA has been notified.

These documents should be retained for a longer period however, if required by the applicable regulatory requirements or if needed by Sponsor or its authorized representative (as per GCP 5.5.11).

At the completion of the study, details of the archival process must be provided to the Sponsor. Study records are subject to inspection by applicable health and regulatory agencies at any time.

Records to be retained by the Investigator include, but are not restricted to:

- Source data and the primary records upon which they are based (e.g., subject's progress notes, adverse event data, test results, and any other diagnostic procedures required to evaluate the progress of the study)
- Completed CRFs
- Signed protocols and protocol amendments
- Laboratory results, ranges, and certifications
- IP and accountability records
- Study personnel signature log
- Monitoring logs
- Correspondence to and from the Sponsor, designee, and IRB
- Investigator and sub-investigator CVs
- Signed informed consent and protected health information consent forms
- Subject screening
- SAE reports
- IRB approval and re-approval letters
- Completed quality of life questionnaire
- Other documents pertaining to the conduct of the study

These documents must be maintained and kept on file by the Investigator so that the conduct of the study can be fully documented and monitored.

Study records should not be transferred from site or destroyed without prior written agreement between the Sponsor and the study Investigator. Study records are subject to inspection by applicable health and regulatory agencies at any time.

14. PUBLICATION PLAN

All information supplied by AIM ImmunoTech Inc. in connection with this study and not previously published, is considered confidential information. This information includes, but is not limited to, the Investigator's Brochure, clinical protocol, case report forms and other scientific data. Any data collected during the study are also considered confidential. This confidential information shall remain the sole property of AIM ImmunoTech Inc., shall not be disclosed to others without the written consent of AIM ImmunoTech Inc., and shall not be used except in the performance of this study.

It is understood by the Investigator that the Sponsor will use the information collected in this clinical trial in connection with the development of AIM ImmunoTech Inc. Therefore, this information may be disclosed as required to other Investigators or appropriate regulatory authorities. By agreeing to participate in this clinical trial, the Investigator understands that he/she has an obligation to provide the Sponsor with complete test results and all data developed during this trial.

Publication and Disclosure: The site and Investigator agree to submit any proposed manuscript, presentation, or other public disclosure regarding the study to Sponsor for review at least thirty (30) days prior to submitting such proposed manuscript to a publisher or delivering or making such presentation or other public disclosure to any third party. Within thirty (30) days of its receipt, Sponsor shall advise the site and/or Investigator, as the case may be, in writing of any information contained therein that is confidential information (other than research results included in a proposed manuscript) or that may impair Sponsor's ability to obtain patent protection. Sponsor shall have the right to require the site and/or Investigator, as applicable, to remove specifically identified confidential information (but may not require removal of research results from a proposed manuscript) and/or to delay the proposed submission or delivery of the proposed manuscript or presentation, or other public disclosure, for an additional sixty (60) days to enable Sponsor to seek patent protection. The site and Investigator shall not publish, publicly disclose, present or discuss any results of or information pertaining to the site's and Investigator's activities prior to completion of the trial, even if the study is terminated before its completion and the final clinical study report is signed off, or with respect to any endpoints or analyses other than those specified in this protocol.

16. APPENDIX

16.1. APPENDIX 1: COMMON TERMINOLOGY CRITERIA FOR ADVERSE EVENTS v5.03

For complete detailed information please refer to the link below:

 $https://ctep.cancer.gov/protocoldevelopment/electronic_applications/docs/CTCAE_v5_Quick_Reference_5x7.pdf$

16.2. APPENDIX 2: PROMIS[®] SLEEP DISTURBANCE – SHORT FORM 4A

Appendix 2 found here.

16.3. APPENDIX 3: PROMIS[®] Cognitive Function-Abilities short form 8A

Appendix 3 found here.

16.4. APPENDIX 4: PROMIS[®] FATIGUE SCALE

Appendix 4 found here.

16.5. APPENDIX 5: SYMPTOM BURDEN QUESTIONNAIRE FOR LONG COVID (SBQ-LC)

Appendix 5 found here.

16.6. APPENDIX 6: PHQ-9 PATIENT DEPRESSION QUESTIONNAIRE

Appendix 6 found here.

16.7. APPENDIX 7: 6-MINUTE WALK TEST

For complete detailed information please refer to the link below:

https://neuropt.org/docs/default-source/cpgs/core-outcome-measures/core-outcome-measuresdrafts--march-2018/6mwt protocol final.pdf?sfvrsn=36cd5443 4

16.8. APPENDIX 8: MONTREAL COGNITIVE ASSESSMENT (MOCA)

16.9. APPENDIX 9: HOLIDAY/VACATION WEEK VISIT SCHEDULING GUIDANCE DOCUMENT

Appendix 9 found here.

1. INTRODUCTION

This Statistical Analysis Plan describes the planned analyses and reporting for the clinical trial protocol AMP-518, conducted by AIM ImmunoTech Inc.. The reader of this Statistical Analysis Plan (SAP) is encouraged to review the complete protocol and amendments as this plan contains only a limited overview of protocol information. The main objectives of this plan are to provide details pertaining to statistical methodology, data conventions, and processes used for the analysis of data from this trial.

The format and content of this SAP are structured to provide sufficient detail to meet the requirements specified by the International Council on Harmonization (ICH) E9: Guidance on Statistical Principles in Clinical Trials. All work planned and presented in this Statistical Analysis Plan will follow the ethical guidelines published by the American Statistical Association (ASA).

The following documents were reviewed in preparation of this Statistical Analysis Plan:

- Protocol Version 4.0/ Aug-23-2023
- ASA Ethical Guidelines for Statistical Practice (2016)
- The Royal Statistical Society: Code of Conduct (2014)
- ICH Guidance on the Structure and Content of Clinical Study Reports (ICH E3, 1996)
- ICH Guidance on the Structure and Content of Clinical Study Reports (ICH E3(R1), 2013)
- ICH Guidance on the Statistical Principles for Clinical Trials (ICH E9, 1998)
- ICH Guidance on the Statistical Principles for Clinical Trials (ICH E9(R1), 2017)

2. PROTOCOL DESIGN

2.1 Design Overview

2.1.1 Study Design

This is a Phase 2, two-arm, randomized, double blind, placebo controlled multicenter study to evaluate the efficacy and safety of Ampligen® in patients experiencing the Post-COVID Condition of fatigue. Patients will be randomized 1:1 to receive twice weekly IV infusions of Ampligen® or placebo.

Ampligen® and placebo will be administered via twice weekly infusions (Example:

Monday/Thursday or Tuesday/Friday schedule) for 12 weeks.

2.1.1.1 Ampligen Dosing Schedule

2.1.1.2 Management of Infusion-Related Reaction

*	
73.	

2.1.1.3 Dosage Modification

2.1.2 Study Visits

2.1.2.1 Study Schedule

The study will have three phases: Screening Phase, Treatment Phase, and Follow-Up Phase.

Screening Phase (up to 1 week):

All subjects will provide written informed consent and have a Screening visit (V1) within 7 days prior to first treatment visit (V2) to determine eligibility for subject participation.

All subjects who fail to meet eligibility criteria are considered screen failures and are exited from the study without further evaluation.

Treatment Phase (12 weeks):

Ampligen[®] and placebo will be administered via twice weekly infusions (Example: Monday/Thursday or Tuesday/Friday schedule) for 12 weeks.

Follow-Up Phase (2 weeks):

Two safety follow-up visits will be performed 3 to 4 days and 2 weeks after the End of Treatment (EOT) visit (V25).

2.1.2.2 Unscheduled Visits

In the event that the subject will return to clinic at a time other than a regularly scheduled study visit, the visit will be regarded as an unscheduled visit. Assessments at unscheduled visits are at the discretion of the Investigator. All pertinent findings, including adverse events or changes in medications, will be noted in the eCRF.

2.2 Treatment Groups

The following treatment groups will be assessed in the study:

- Ampligen[®]
- Placebo (normal saline)

2.3 Randomization and Stratification

A total of 80 subjects (40 per group) will be randomized in a 1:1 ratio (Ampligen[®]:

2.4 Blinding

This is a double-blind study. The investigator and staff, subjects and Sponsor/CRO staff directly related to study conduct will be blinded to the treatment assignment.

2.4.1 Emergency Un-Blinding

Breaking the blind prematurely will be allowed only if the subject's well-being requires knowledge of the subject's treatment allocation. Every attempt will be made to maintain the blind throughout the study.

2.5 **Protocol Objective(s)**

The purpose of this study is to assess the efficacy and safety of Ampligen® administered twice weekly by IV infusions in subjects experiencing the Post-COVID Condition of fatigue.

2.6 Efficacy Outcome Measures

2.6.1 Primary Efficacy Outcome Measure

• Change from baseline to week 13 in PROMIS[®] Fatigue Score (T-Score).

2.6.2 Secondary Efficacy Outcome Measures

• Change from baseline to week 6 in PROMIS[®] Fatigue Score (T-Score).

Note: Additional PROMIS® Fatigue Score analysis (change from baseline) at week 6 and 13 will be performed excluding response to item, "How often did you have enough energy to exercise strenuously?"

- Change from baseline to week 6 and 13 in distance traveled during a 6-minute walk test.
- Proportion of subjects with minimal clinically important difference (MCID), defined as at least 54 m, in the Six-Minute Walk Test (6MWT) at the end of 12-week treatment phase.
- Change from baseline to week 6 and 13 in PROMIS[®] Cognitive Function Score (T-Score).
- Change from baseline to week 6 and 13 in PROMIS[®] Sleep Disturbance Score (T-Score).

2.6.3 Exploratory Outcome Measures

• Changes from baseline in COVID-19-related symptoms using Symptom Burden Questionnaire for Long COVID (SBQ-LC) during the course of the treatment phase.

Note: A set of common COVID-19-related symptoms (see Symptom Burden Questionnaire for Long COVID (SBQ-LC)) will be evaluated at each scheduled study visit by the patient regardless of which symptoms a subject had at baseline, as new symptoms may appear following the baseline assessment.

- Change from baseline in cognitive function as measured by Montreal Cognitive Assessment (MoCA) at week 4, 8, and 13 during the treatment phase.
- Incidence of hospitalization during the treatment phase.
- Duration (days) of hospitalization during the treatment phase.
- Evaluation of lymphocyte profile by flow cytometry in patients with post-COVID-19 conditions.

• Identification and evaluation of plasma protein biomarkers in patients with post-COVID-19 conditions.

2.6.4 Safety Outcome Measures

- Incidence of treatment-related adverse events.
- Incidence and severity of treatment-emergent adverse events (TEAEs).
- Incidence of serious adverse events (SAEs).
- Incidence of TEAEs and SAEs leading to discontinuation of study medication.
- Changes in blood chemistry, hematology, and coagulation results.
- Changes in vital signs including temperature, pulse, respiratory rate, systolic and diastolic blood pressure.
- Changes in physical examination results.
- Change in electrocardiogram (ECG) results.

3. SAMPLE SIZE DETERMINATION, STATISTICAL POWER, AND SIGNIFICANCE LEVEL

The sample size of 80 subjects will be used in this study. The sample size is based on clinical judgment. No statistical power calculation is used to establish the sample size for this proof-of-concept study.

4. INTERIM ANALYSIS

There is no planned interim analysis for this early phase study.

5. PRIMARY HYPOTHESIS TO BE TESTED

There is no formal hypothesis testing for this study as the study is a Phase II evaluation and is not intended to be hypothesis generating. The study is not powered to reliably yield statistically significant conclusions.

6. ANALYSIS POPULATIONS

7. DATA CONVENTION AND RELATED DEFINITIONS

7.1 Baseline Definition

For all parameters, baseline will be defined as the last available value before the first randomized treatment.

7.2 Duplicate Data

7.3 Handling of Missing Data

7.3.1 Handling of Missing Data for Efficacy Evaluations

Every effort will be made to obtain required data at each scheduled evaluation from all subjects who have been randomized to minimize missing data.

7.3.2 Handling of Missing Data for Safety Evaluations

The below imputation rules will be followed for imputation of missing dates:

7.4 Multicenter Clinical Trials

This is a multi-center clinical trial.

7.5 Multiple Comparisons and Multiplicity

There will be no adjustment for multiple testing or multiplicity for this phase II trial. For all effectiveness endpoints, inference will be based on type I error rate of 0.05.

7.6 Covariates and Prognostic Factors

In the efficacy analysis, the stratification factors and baseline values will be used as

covariates in the analysis of all the primary, secondary, and additional efficacy endpoints.

7.7 Subgroups

7.8 Standard Calculations

7.8.1 Body Mass Index (BMI)

BMI will be calculated using height (in cm) and weight (in kg) according to the formula noted below.

BMI $(kg/m2) = Weight (kg)/[Height (cm)/100]^2$

7.8.2 Change from baseline

Change from baseline will be calculated for each post baseline visit as follows:

Change From Baseline = Post baseline result at time - Baseline result

7.8.3 Duration (days) of hospitalization during the treatment phase

The duration (days) of hospitalization during the treatment phase will be calculated using the formula noted below.

Duration (days) = (Date of discharge - Date of hospitalization) + 1Duration (days) of hospitalization during the treatment phase will only be calculated for hospitalization(s) occurring after the date of first study treatment administration and prior to the date of last study treatment administration. For subject who remain hospitalized at the time of last treatment administration, the date of last treatment will be used for the calculation.

All deaths within 91 days will be considered censored on Day 91. Conceptually, a death corresponds to an infinite length of hospitalization but censoring at any time greater than or equal to Day 91 gives the same answer as censoring at Day 91; both correspond to giving deaths the worst rank.

In the incidence where there are multiple hospitalizations for a subject, the durations from the multiple hospitalizations will be summed to provide total duration of hospitalization for the subject.

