8.2.3.3 Incidence of hospitalization during the treatment phase

The proportion of subjects with at least one hospitalization during the treatment phase will be presented for the two treatment groups.

Similar

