8.2.3.4 Duration (days) of hospitalization during the treatment phase

The duration (days) of hospitalization during the treatment phase will be calculated using the formula stated in Section 7.8.4.

8.2.3.5 Evaluation of lymphocyte profile by flow cytometry in patients with post-COVID-19 conditions

analysis methods used for the primary endpoint will be applied to analyze the data from this outcome measure.

8.2.3.6 Identification and evaluation of plasma protein biomarkers in patients with post-COVID-19 conditions

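### SAP 7.8.3 stops counting hospital days at the last infusion, so a non-fatal stay that ends treatment is dropped or cut while the same stay counts in full if infusions resume

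*SAP*

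**What the plan says.** SAP 2.6.3 lists "Duration (days) of hospitalization during the treatment phase" as an exploratory outcome. SAP 7.8.3 defines it as discharge date minus admission date plus 1, summed over stays, and restricts it to "hospitalization(s) occurring after the date of first study treatment administration and prior to the date of last study treatment administration". A stay that is still open is truncated: "For subject who remain hospitalized at the time of last treatment administration, the date of last treatment will be used for the calculation". The one visible exception is for deaths: "All deaths within 91 days will be considered censored on Day 91". The SAP explains that this gives deaths the worst rank.

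SAP 2.1.2.1 gives the Treatment Phase as 12 weeks. SAP 8 runs the efficacy analyses on the mITT and PP populations, and SAP 8.2.1.2 admits to the mITT population any subject with at least one dose. For the companion incidence endpoint, the visible text of SAP 8.2.3.3 reads "The proportion of subjects with at least one hospitalization during the treatment phase will be presented for the two treatment groups". SAP 8.2.3.4 refers for the duration to the "formula stated in Section 7.8.4", although the formula stands in 7.8.3. The analysis method for duration is not visible.

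**The concern.** The counting window closes at each subject's last infusion, which is an event after randomization that a hospital stay can bring about. Under Protocol 9.3, an adverse event that requires hospitalization is serious. Protocol 5.2 gives a serious event judged related to study drug, and intercurrent illness or surgery, as examples of reasons for stopping treatment. A stay that ends treatment is therefore the kind of stay that the rule leaves out or shortens. Deaths within 91 days are protected by the ranking rule, so the gap concerns non-fatal stays.

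What is at stake is the between-arm comparison of this one endpoint. If stays that end treatment are more frequent in one arm, the two arms are compared over windows of unequal length, and the inequality is related to the outcome.

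**Working it through.** The plan states no figure to reproduce, so the check applies the rule of SAP 7.8.3 to illustrative stays.

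**Inputs.** V2 is Day 0 (Protocol 4.2.1). Infusions are twice weekly for 12 weeks, V2 to V25, which makes 24 doses. Alternating gaps of 3 and 4 days are assumed. Odd-numbered doses then fall on multiples of 7: dose 3 on Day 7, dose 9 on Day 28, dose 13 on Day 42, dose 17 on Day 56. Dose 24 falls on Day 11 × 7 + 3 = 80 or 11 × 7 + 4 = 81. The stays are invented and non-fatal.

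**Rule.** A stay is calculated if first infusion < admission < last infusion. Days = min(discharge, last infusion) − admission + 1.

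| Stay | Last infusion | Days calculated |
|---|---|---|
| Days 30–40 | Day 42 or later (dosing resumes) | (40 − 30) + 1 = 11 |
| Days 30–40 | Day 28 | none |
| Days 27–40, infusion on Day 28 | Day 42 or later (dosing resumes) | (40 − 27) + 1 = 14 |
| Days 27–40, infusion on Day 28 | Day 28 | (28 − 27) + 1 = 2 |

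**Edges of the window.**
- Admission on the last-infusion date is ambiguous. The restriction excludes it, while the truncation sentence can be read as giving 1 day. Neither gives the full stay unless discharge is on that same day.
- A last infusion on the discharge day also yields the full count, so resumption after discharge is not strictly required.
- Admission on the first-infusion date is excluded if the stay is dated by admission. The wording is loose here.

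**Length of the window.** With the last infusion on Day L, an admission can qualify on L − 1 days: 7 − 1 = 6 after dose 3, 28 − 1 = 27 after dose 9, 56 − 1 = 55 after dose 17, and 79 or 80 after all 24 doses. After a single infusion the first and last dates coincide and the window is empty, yet the subject is in the mITT population. These are window lengths, not effects on the endpoint.

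**Scale at arm level, by assumption only.** Take 40 subjects in an arm, one to three stays of 11 days, and uncalculated stays entered as 0. If dosing resumes in all of them, the arm mean is 1 × 11/40 = 0.275 to 3 × 11/40 = 0.825 days per subject. If it resumes in none and each stay began after the last infusion, the mean is 0.

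**Fixed window.** With any common end day from Day 40 onwards, the two stays count 11 and 14 days whether or not dosing resumes.

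**The case against.** The strongest defence is that this is a choice of estimand: hospital days while on treatment. Protocol 9.2.1 can be read as letting a subject leave the Treatment Phase early, and SAP 7.8.3 may simply define the phase as first to last administration. That explains leaving out a stay long after dosing has stopped. It does not explain excluding, in retrospect, a stay that began two days after an infusion while further infusions were still scheduled.

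The limits on importance stand. The endpoint is exploratory, and SAP 5 says "There is no formal hypothesis testing for this study" (although SAP 7.5 refers to inference at 0.05 for all effectiveness endpoints). The admissions themselves are not lost. They are serious adverse events, SAP 8.3.1 tabulates adverse events leading to treatment discontinuation by arm, and all data are listed. What goes missing is their length in this measure.

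Three stronger readings are tempting and are not supported:
- A reader might infer that the rule always flatters the arm with more stays that end treatment. That follows only if an uncalculated stay enters as 0. If it is missing, the direction is not determined, and the visible text does not say which applies.
- A reader might infer that the incidence endpoint deliberately uses a wider window. The text of SAP 8.2.3.3 breaks off, so the absence of date limits there shows nothing.
- A reader might take the Day 91 rule as evidence that a fixed observation window was intended. The SAP itself says that any later day would give the same answer, because the rule only ranks deaths.

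**Conclusion.** The point holds for this endpoint, on the natural reading that the administration dates are each subject's own. A non-fatal stay that begins after the last infusion is not calculated, and one still open at the last infusion is cut there. The identical stay counts in full if infusions resume: 11 days against none, or 14 against 2, in the examples. Because a hospitalization can itself end treatment, the comparison between arms can be biased if such stays differ by arm. If uncalculated stays enter as 0, the bias favours the arm with more of them.

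No effect size can be given, because the documents contain no hospitalization or discontinuation rate. The primary result is unaffected. The rule should be changed because it is written into the plan and is cheap to correct, not because it threatens the main conclusion.

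**What to change.** In SAP 7.8.3, replace the limits at first and last administration with one fixed window for every dosed subject:

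- Start on the first-infusion date, inclusive. End at the close of the 12-week Treatment Phase counted from V2, written as one study day for all subjects, whether or not treatment stopped and whether or not V25 was moved. With V2 as Day 0, 12 × 7 = 84 days run from Day 0 to Day 83.
- Cut stays still open on that day, or at last contact if earlier.
- Score subjects observed with no stay as 0. Report by arm the observed days within the window and the number of subjects not observed to its end, including those with no known stay, so that they are not silently treated as fully observed.
- Keep the death rule.
- Apply the same window to the incidence endpoint in SAP 8.2.3.3, and check the reference to Section 7.8.4 in SAP 8.2.3.4.

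The cost is SAP wording and a small reprogramming. Hospital-day totals may rise. A completer's stay after the fixed day will not count, even if a late V25 would have brought it in under the present rule. Observation will still be shorter for subjects lost to follow-up, but it will be reported. Protocol 5.4 and 9.4.1 seek information after treatment stops, but no visible text names admission and discharge dates as collected fields, so their capture after discontinuation must be confirmed.
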